## 14.0 Body Fluid and Tissue Biospecimens

Body fluid and tissue biospecimens will be obtained both pre- and post-treatment.

Blood: 2 vials of whole blood, each 10 ml, drawn in purple top EDTA tubes (blood card specifies 2 - 10ml EDTA tubes). BAP will accession and label. Aliquot (1) 4000uL blood pour for DNA extraction. Refrigerate. Centrifuge at lab standards.

**First EDTA vial** should be processed for three 1 ml aliquots of plasma into 3 cryovials 1 ml plasma each and 1ml WBC. **Second EDTA vial** is stored as whole blood.

Freeze products from both vials. Post-treatment only-One 4 ml. vial of whole blood, drawn in green top heparin tube, processed for plasma. Stored at -80 freezer.

Tissue: Core biopsies or surgical tissue will be used to create two snap frozen samples and a single paraffin block (if applicable).

For more details, please see individual sections above as follows:

Pre-Treatment Blood Samples- section 6.8.2.

Pre-Treatment Tissue Samples- section 6.8.3.

Post-Treatment Biopsy- section 7.3.

Post-Treatment Blood Samples- section 7.4

**15.0 Summary Table of Research Blood and Tissue Specimens to be Collected for this Protocol**

Research	Specimen Purpose	Mandatory or Optional	Blood or Body Fluid being Collected	Type of Collection Tube (color of tube top)	Volume to collect per tube (# of tubes to be collected)	Pre-Intervention	Post - Intervention
Blood	Banking	Mandatory	Whole blood - Aliquot (1) 4000uL blood pour for DNA extraction. Refrigerate. Centrifuge at lab standards. First EDTA vial should be processed for three 1 ml aliquots of plasma into 3 cryovials 1 ml plasma each and 1ml WBC. Second EDTA vial is stored as whole blood. Freeze. Light Sensitive	Purple/ EDTA	10 mL (2 tubes)	X	X
Blood	4-OHT levels	Mandatory	One 4 ml green top heparin tube will be used for 4-OHT levels. This tube is to be wrapped in tin foil due to light sensitivity. The tube will need to be processed for plasma and stored in - 80 freezer.	Green/ Heparin	4 mL		X
Breast Tissue Pre Treatment from Diagnostic Clinical Biopsy	Ki67 and RNA extraction	Mandatory if opting out of PreTreatment Research Biopsy	PreTreatment- 6 5 micron FFPE sections for H&E and Ki67, and to be determined IHC biomarker assays 3 10 micron FFPE sections for RNA extraction	FFPE	FFPE sections. See pathology manual for details of cores per tube, processing, and handling.	X	

Breast Tissue PreTreatment Research Biopsy	banking	Optional	
4 vacuum assist cores- either 9 or 11 G
 
For
 
PreTreatment-Two cores snap frozen for RNA; two cores in formalin for single FFPE block
 
The remaining cores/pieces placed in formalin and processed into 1 paraffin block if possible
	Sterile	3 tubes-2 snap frozen, 1 in formalin. See pathology manual for details of cores per tube, processing, and handling.	X	
Breast Tissue Post Treatment	banking	Mandatory	
4 vacuum assist cores- either 9 or 11 G
 
For tissue taken during surgery two 1 cm^2 pieces.
 
Post-Treatment- Two cores / tissue pieces snap frozen; one for 4OHT levels (see row below) and one for RNA extraction
 
The remaining cores/pieces placed in formalin and processed into 1 paraffin block if possible
	Sterile	3 tubes-2 snap frozen, 1 in formalin. See pathology manual for details of cores per tube, processing, and handling.		X
Research	Specimen Purpose	Mandatory or Optional	Blood or Body Fluid being Collected	Type of Collection Tube (color of tube top)	Volume to collect per tube (# of tubes to be collected)	Pre-Intervention	Post - Intervention

Breast Tissue	4-OHT levels	Mandatory	One core/piece snap frozen for 4-OHT levels	Sterile	1 tube-see pathology manual for details.		X
---------------	--------------	-----------	---------------------------------------------	---------	------------------------------------------	--	---

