## **3.0 Goals**

- 3.1 Primary Aim.** Change in Ki67 from pre-treatment to post-treatment
- 3.2 Secondary Aims.** Changes from pre-treatment to post-treatment in:
  - Mammographic volumetric % density
  - Mammographic dense volume
  - Breast Cancer Prevention Trial Symptom Survey
  - Molecular Breast Imaging background parenchymal uptake
  - Changes in novel tissue biomarkers from our previous work; will be assessed with NanoString and immunohistochemistry
  - 4-OHT and metabolite levels in blood and tissue
  - Coagulation parameters

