8. Pretreatment (baseline OPTIONAL) research tissue. This is optional if the subject has a pretreatment diagnostic breast biopsy that is 1) within 6 months of enrollment, 2) no exogenous sex steroids other than vaginal estrogen or hormone coated IUD within one month prior to the diagnostic biopsy, 3) has at least 4 normal TDLUs by pathologist review, and 4) if the FFPE tissue from the diagnostic biopsy will be available to the research study for primary (Ki67) and secondary tissue endpoints (RNA extraction). If Pretreatment research biopsy is performed, tissue will be collected by doing vacuum assist core biopsy, using a 9-11G needle. At Mayo Clinic, snap frozen tissues will be stored in BAP, and batch shipped to [name] lab in Jacksonville, FL; formalin fixed cores will be delivered to the Clinical Histology lab to create a single FFPE block if possible and a single H&E stain for each block. The H&E stained slide(s) will be delivered by the study coordinator to the breast pathologist, [name], or her designee, for core biopsy read within 21 days of biopsy. After the breast pathologist's review is complete, the FFPE blocks and H&E will be stored and batch shipped to [name] lab in Jacksonville, FL for Ki67 IHC, slide scanning at 40X, and Aperio quantitation. At Northwestern University and MD Anderson Cancer Center at Cooper, snap frozen cores will be stored at -80, and shipped to [name] lab in Jacksonville; formalin fixed cores will be put up as a single FFPE block if possible (see details section 6.8.3). (Note, there will not be 4OHT testing on pretreatment breast tissue samples.)

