## **7.3 Post-Treatment Biopsy**

### **7.3.1 Core Biopsy**

**See Appendix F for details on post treatment core biopsy.**

At Mayo Clinic, the two snap frozen cores will be delivered to BAP by the study coordinators. After accessioning, [name] lab will be paged to pick up and store tissue for tamoxifen/4-OHT levels; and the other snap frozen core will be stored and sent to [name] lab for RNA extraction; the remaining two cores will be put in formalin for a single FFPE block if possible. [name] lab will additionally need to know the date and time of the last dose of tamoxifen/placebo and 4-OHT/placebo.

At Northwestern University and MD Anderson Cancer Center at Cooper, two of the largest cores will be distributed between 2 separate tubes and snap frozen (1 core per tube), one tube is designated for [name] lab and the other is designated for [name] lab. These will be stored at -80 and will then be batch shipped to Mayo Clinic Rochester BAP and [name] laboratories respectively. The remaining cores will be put up as a single FFPE block (if possible) and shipped to [name] lab also in batches.

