### **7.3.2 Surgical Biopsy**

If the patient will undergo excisional biopsy, the post-treatment tissue samples can be taken at the time of surgery. Two 1 cm^2 pieces of tissue will be needed. One of these will be put in formalin for a single FFPE block; the other tissue piece should be cut in half and placed into two separate sterile tubes for snap freezing.

One of these two cut pieces will be snap frozen and designated for [name] lab for tissue tamoxifen/4-OHT levels), and the other will be snap frozen and designated for [name] lab for RNA extraction.

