*Statistical analysis.* The primary hypothesis is that the reduction seen with 4-OHT gel will be *not inferior* to that seen with oral tamoxifen. We also hypothesize that oral tamoxifen and 4-OHT gel will each be superior to placebo with respect to the percent change in Ki67 in background normal lobules between baseline and four weeks. Analyses will assess if significant changes in Ki67 are observed after four weeks of treatment by paired t-tests/Wilcoxon signed rank tests, stratified by treatment group. We will assess the non-inferiority of 4-OHT gel compared to oral tamoxifen by estimating a 95% confidence interval for the mean *difference* in percent change between the two agents after four weeks of treatment; if the lower limit of the confidence interval is less than the non-inferiority margin (described below), we will conclude that 4-OHT gel is non-inferior to oral tamoxifen. As exploratory analyses, we will assess pairwise differences between samples on active treatment (oral tamoxifen or 4-OHT gel, separately and combined) vs. placebo using two-sample t-tests/Wilcoxon rank sum tests. Similarly, we will assess changes from baseline in the expression of the candidate genes identified in Aim 2 (absolute log2 fold-change > 2 and/or q-value < 0.05). Volumetric density changes from baseline within treatment group will be assessed continuously, and evaluated using paired t-tests on the log-transformed density or Wilcoxon signed-rank tests; pairwise differences between treatment groups will be assessed with two-sample t-tests/Wilcoxon rank sum tests. BPU on MBI is measured as a four category ordinal scale; we will compare pre-to-post changes within group using Wilcoxon signed rank tests and will compare the percent of subjects decreasing BPU category by one or more level between groups using chi-square tests. We will assess the correlation between changes in volumetric density and changes in BPU, using Spearman correlation. Symptoms from the BCPT survey are measured on a five-level ordinal scale. We will compare differences in pre- to post-treatment symptom severity changes across

treatment arms using Wilcoxon rank sum tests.

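### Women whose baseline is the diagnostic biopsy have FFPE RNA before treatment and snap-frozen RNA after it, so their within-arm change in gene expression cannot be separated from preservation method

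*Combined protocol and SAP*

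**What the plan says.** Section 3.0 lists among the secondary aims, as pre- to post-treatment changes: "Changes in novel tissue biomarkers from our previous work; will be assessed with NanoString and immunohistochemistry". Section 11.0 plans the analysis: "we will assess changes from baseline in the expression of the candidate genes identified in Aim 2".

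The source of RNA depends on the route and the time point:

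- **Baseline, research biopsy done.** Section 15.0: "Two cores snap frozen for RNA; two cores in formalin for single FFPE block".
- **Baseline, research biopsy skipped.** The diagnostic tissue is then required ("Mandatory if opting out of PreTreatment Research Biopsy", Section 15.0), and what is taken for expression work is "3 10 micron FFPE sections for RNA extraction". Footnote 8 of Section 5.0 makes this a condition of skipping: the biopsy is optional only "if the FFPE tissue from the diagnostic biopsy will be available to the research study for primary (Ki67) and secondary tissue endpoints (RNA extraction").
- **After treatment, needle core.** Section 7.3.1 sends one frozen core for drug levels, and "the other snap frozen core will be stored and sent to [name] lab for RNA extraction".
- **After treatment, surgery.** Section 7.3.2 halves one tissue piece; one half goes for drug levels, and "the other will be snap frozen and designated for [name] lab for RNA extraction".

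A post-treatment FFPE block is also made (footnote 9 of Section 5.0, and Sections 7.3.3 and 15.0). It is directed to Ki67 staining and image quantitation. No section directs it to RNA.

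**The concern.** A change from baseline can be read as biology only if the two measurements differ in time and treatment and in nothing else that moves the result systematically. On the diagnostic-biopsy route the preserved material changes at exactly the point where treatment intervenes. If a transcript reads differently in FFPE and frozen material, every woman on that route carries the offset, in every arm, and a within-arm test cannot tell it from a drug effect. Multiplicity control does not remove it, because the offset is a real non-zero mean shift and not chance.

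At stake is the interpretation of one secondary aim. Section 11.0 has no term for preservation method, no rule that pairs must match and no sensitivity analysis by baseline source. Section 6.0 does not stratify by baseline source.

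**Working it through.** **Step 1: the specimen rules side by side.**

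| Route | Baseline RNA | Post-treatment RNA | Measured change |
|---|---|---|---|
| Research biopsy | snap-frozen cores | snap-frozen core or piece | frozen minus frozen |
| Diagnostic biopsy | three 10 micron FFPE sections | snap-frozen core or piece | frozen minus FFPE |

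No section supplies frozen baseline tissue on the second route, or FFPE-derived RNA after treatment on either. For Ki67 the material is FFPE at both times on both routes.

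**Step 2: what is being tested.** The plan gives no sample size, power or error rate for gene expression, so there is no figure of its own to reproduce. The only input taken from the documents is n = 36 per active arm (Section 11.0). Three inputs are assumptions, because the documents are silent:

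- f, the share of an arm on the diagnostic-biopsy route: 0.10 to 0.75;
- d, the FFPE-to-frozen offset in log2 units: 0.1 to 1.0;
- the SD of paired log2 change within a route: 1.

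**Step 3: formulas, with no drug effect.**

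- Spurious mean change = f × d.
- SD of change = √(1 + f(1 − f)d²).
- Noncentrality = √36 × f × d / SD.
- False-positive rate = rejection probability of a two-sided 0.05 paired t-test on 35 degrees of freedom.

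Worked case, f = 0.5 and d = 0.5: mean = 0.25; SD = √(1 + 0.25 × 0.25) = 1.031; noncentrality = 6 × 0.25 / 1.031 = 1.455; rejection probability 29%.

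| f | d | Spurious mean change | False-positive rate per gene |
|---|---|---|---|
| 0.10 | 0.1 | 0.01 | 5% |
| 0.10 | 0.5 | 0.05 | 6% |
| 0.25 | 0.25 | 0.0625 | 6.5% |
| 0.25 | 0.5 | 0.125 | 11% |
| 0.5 | 0.25 | 0.125 | 11% |
| 0.5 | 0.5 | 0.25 | 29% |
| 0.5 | 1.0 | 0.50 | 74% |
| 0.75 | 1.0 | 0.75 | 98% |

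The assumed SD matters as much: at f = 0.5 and d = 0.5 the rate is 16% if the SD is 1.5 and 74% if it is 0.5.

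**Step 4: between arms.** The offset has the same expected size, f × d, in each arm and cancels in expectation. Simulation with 36 per arm gave between-arm false-positive rates of 4.7% to 5.2% over f from 0.25 to 1 and d from 0.25 to 2. What remains is extra variance, f(1 − f)d²: 0.0625 on a base of 1 (6%) at f = d = 0.5, and 0.25 (25%) at f = 0.5, d = 1.0.

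**The case against.** The best reply is that the consequence is assumed. Nothing in the documents says how large an offset would survive processing, or how many women take this route. Footnote 8 sets four conditions for it (biopsy within 6 months, no recent exogenous sex steroids apart from the permitted vaginal and IUD forms, at least 4 normal TDLUs, FFPE tissue available), while Section 4.1.6 admits women whose histology is up to 5 years old or who have no lesion at all. The share could be small. This stands, and it is why the range above begins at the nominal 5%.

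Second, the test computed is not the plan's rule. Section 11.0 names a q-value below 0.05 and/or an absolute log2 fold-change above 2. A q-value is multiplicity-adjusted, and a spurious mean of 0.25 to 0.75 would very rarely pass the fold-change limit. The parenthesis may even describe how the Aim 2 candidates were chosen. So a reader should not take 29% or 74% as error rates under the plan.

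Third, a reader might infer that the trial will report preservation artefacts as drug effects. The documents do not support that. There is a concurrent double-placebo arm that would show the same offset, and the gene sentence opens with a word linking it to the active-versus-placebo comparisons just before it, so a between-arm analysis is a plausible reading. Diagnosis, which is linked to route, is a stratification factor. But Section 11.0 states no explicit between-arm gene test, and the quantity it names is change from baseline.

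Fourth, it is tempting to add that diagnostic sections contain the atypical lesion while post-treatment tissue does not. That is inference. The study's stated interest is background tissue, footnote 8 requires normal TDLUs, and Section 15.0 defers handling to a pathology manual not included here. It is a caution, not an established error.

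None of this reconciles the specimen rules themselves.

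**Conclusion.** The mismatch is certain on the text: followed exactly, the plan makes change from baseline frozen minus FFPE for every woman on the diagnostic-biopsy route. Within-arm changes that include these women are confounded with preservation method. Between-arm differences are unbiased in expectation but less precise.

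The size is unknown. The illustration spans about 5% (10% of women, offset 0.1 log2) to 98% (75% of women, offset 1.0) per gene, and rests on an assumed SD of 1, additive offsets and an unadjusted test. It shows direction and sensitivity only.

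This should be corrected, but it is a limited point: one secondary aim without a stated power, in an unstated subset of women. It does not reach the Ki67 primary endpoint, and it does not invalidate gene expression in women with frozen tissue at both times.

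**What to change.** **Specimen sections (6.8.3, 7.3 and 15.0).** State that paired RNA change uses the same material at both times. For women with an FFPE baseline, cut three 10 micron sections from the post-treatment FFPE block once the sections for Ki67 are secured. Use frozen-frozen pairs for the others. In the same edit, reconcile Section 6.8.3, which lists the 10 micron diagnostic sections as shipped for Ki67 work, with Section 15.0, which assigns them to RNA.

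**Section 11.0.**

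- Analyse gene expression stratified by material, or adjust for baseline source.
- Rest drug-effect conclusions for genes on between-arm differences in change, including placebo.
- Add a sensitivity analysis restricted to frozen-frozen pairs.
- Where matched FFPE RNA cannot be obtained, keep the mixed pair out of the within-arm change test.
- Say whether the fold-change and q-value limits define the candidate genes or call a change.

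**Cost.** No new procedure for participants: the block is already planned and goes to the same laboratory as the RNA tissue. The price is a few more sections and extractions, some block tissue that competes with Ki67 and other staining, and possibly noisier RNA from FFPE. It is best settled before blocks are used up or RNA is run.

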## 16.0 Remuneration

Participants will receive remuneration of \$350-500. This will be prorated as follows: \$150 upon completion of the optional baseline study biopsy, and \$350 upon completion of study intervention and post-treatment biopsy. All Participants will also receive a small gift of appreciation.

## APPENDIX A

### Performance Status Criteria

#### ECOG Performance Status Scale

Grade	Descriptions
0	Normal activity. Fully active, able to carry on all pre-disease performance without restriction.
1	Symptoms, but ambulatory. Restricted in physically strenuous activity, but ambulatory and able to carry out work of a light or sedentary nature (e.g., light housework, office work).
2	In bed <50% of the time. Ambulatory and capable of all self-care, but unable to carry out any work activities. Up and about more than 50% of waking hours.
3	In bed >50% of the time. Capable of only limited self-care, confined to bed or chair more than 50% of waking hours.
4	100% bedridden. Completely disabled. Cannot carry on any self-care. Totally confined to bed or chair.
5	Dead.

#### Karnofsky Performance Scale

Percent	Description
100	Normal, no complaints, no evidence of disease.
90	Able to carry on normal activity; minor signs or symptoms of disease.
80	Normal activity with effort; some signs or symptoms of disease.
70	Cares for self, unable to carry on normal activity or to do active work.

Percent	Description
60	Requires occasional assistance, but is able to care for most of his/her needs.
50	Requires considerable assistance and frequent medical care.
40	Disabled, requires special care and assistance.
30	Severely disabled, hospitalization indicated. Death not imminent.
20	Very sick, hospitalization indicated. Death not imminent.
10	Moribund, fatal processes progressing rapidly.
0	Dead.

## Appendix B

### Breast Cancer Prevention Trial Symptom Checklist

#### EVERYDAY PROBLEMS DURING THE PAST 4 WEEKS

---

We are interested in knowing how much you have been bothered by any of the following problems during the **PAST 4 WEEKS**. (Circle one number on each line. If you do not have the problem, circle "not at all".)

During the past 4 weeks, how much were you bothered by:

	Not at All	Slightly	Moderately	Quite a Bit	Extremely
1. Hot flashes	0	1	2	3	4
2. Nausea	0	1	2	3	4
3. Vomiting	0	1	2	3	4
4. Difficulty with bladder control when laughing or crying	0	1	2	3	4
5. Difficulty with bladder control at other times	0	1	2	3	4
6. Vaginal dryness	0	1	2	3	4
7. Pain with intercourse	0	1	2	3	4
8. General aches and pains	0	1	2	3	4
9. Joint pains	0	1	2	3	4
10. Muscle stiffness	0	1	2	3	4
11. Weight gain	0	1	2	3	4
12. Unhappy with appearance of my body	0	1	2	3	4
13. Forgetfulness	0	1	2	3	4
14. Night sweats	0	1	2	3	4
15. Difficulty concentrating	0	1	2	3	4
16. Easily distracted	0	1	2	3	4
17. Arm swelling (lymphedema)	0	1	2	3	4
18. Decreased range of motion in arm on surgery side	0	1	2	3	4
19. Vaginal Discharge	0	1	2	3	4
20. Vaginal bleeding or spotting	0	1	2	3	4
21. Genital itching/irritation	0	1	2	3	4
22. Lack of energy	0	1	2	3	4
23. Tiredness	0	1	2	3	4
24. Lack of interest in sex	0	1	2	3	4
25. Low sexual enjoyment	0	1	2	3	4

## **Appendix C**

### **Instructions Oral Tamoxifen**

1. Take your pill at the same time every day.
2. If you miss a dose, take the dose as soon as you remember unless it is almost time for your next dose. If it is almost time for your next dose, wait until then and take a regular dose. Mark the missed dose on the calendar provided. Do not take a double dose.
3. You can take the pill with or without food. There are no specific foods to avoid.
4. If you start any new medication while you are on study, please call your study coordinator at [name] to let them know. She will check with the study doctor and your personal physician so that possible interactions are managed safely.
5. If you develop hot flashes, some suggestions for managing them:
  - Dress in layers, avoid turtlenecks, wool and synthetic material.
  - Keep your bedroom cool.
  - Avoid alcohol, caffeine, hot or spicy foods.
  - Avoid hot tubs, hot showers and saunas.
  - Engage in physical activity such as walks.

## Appendix D

### Instructions 4-OHT Gel Application

1. The gel is flammable while in gel form: do not apply near fire, flame, heat or smoke. Once dry, the gel is not flammable.
2. Prior to applying gel, shower or wash breasts with a washcloth and dry thoroughly.
3. Remove the cap, point the canister toward the sink or a wastebasket, prime the canister by pushing on the pump all the way several times until gel is dispensed. Do not use the first dose as it may not be a full dose.
4. If you don't push the pump all the way or you discard more than one dose, discard the pumped doses and record this in your diary.
5. Pump one dose into the palm of your hand and make sure to release pump completely between doses.
6. Spread the gel evenly across your entire breast, without rubbing.
7. Repeat for the other breast.
8. After the gel is dry, apply a second pump of gel to each breast.
9. Wash your hands immediately with soap and water.
10. Replace the cap on the canister.
11. Allow the gel to air dry for 2 minutes and then cover immediately with clothing. The gel is colorless and will not stain clothing.
12. Do not wash your breasts or immerse in water for a minimum of 4 hours after application. If this is not possible, delay application until after immersion, such as after you swim.
13. If you miss a dose, do not double the dose. If your next dose is within 12 hours, skip it, note it on the provided calendar and just resume the gel at the next scheduled time. If your next dose is more than 12 hours later, apply the missed dose and resume your normal dose at the next scheduled time.
14. Mark on each canister the date and the time of your first dose.
15. Keep the canisters at room temperature and keep out of the reach of children.
16. Do not expose treated area to sunlight at any time.
17. For the duration of the study, do not apply any other cream, lotion, or moisturizer to your breasts at any time.
18. Avoid contact between the application area and the skin of another person. Skin contact is allowable after area is washed. However, don't wash this area for at least 4 hours after application.
19. At the end of the study bring the canisters back with you to your follow-up visit with the study coordinator.

